4.2 SCIENTIFIC RATIONALE FOR STUDY DESIGN

The proposed study aims to establish proof-of-concept that non-alpha IL-2 SAR444245 combined with other anticancer therapies, or as monotherapy, in trial participants with relapsed or refractory B cell lymphoma.

The design of the study is a non-randomized study where the experimental combination or monotherapy will be assessed in a single cohort for each indication, using historical data for single agent as a benchmark to show outstanding objective response rate. The primary endpoint will be assessed using Lugano response criteria 2014 for participants with relapsed or refractory B cell lymphoma. It will be assessed per Investigator. Central imaging reading may be done retrospectively if significant activity is observed.

A safety run-in on the first 6-10 participants being enrolled in the individual substudy has been embedded in the study to confirm the absence of safety issues before launching enrollment of the remaining participants in a specific cohort.

4.2.1 Participant input into design

Teenagers with a history of lymphoma and their parents participated in an advisory panel, reviewed the study design, and provided input.

4.3 JUSTIFICATION FOR DOSE

Dose escalation for SAR444245 monotherapy and in combination with pembrolizumab or cetuximab is ongoing in the first-in-human HAMMER study. Data from a total of 68 patients who have received SAR444245 Q2W or Q3W in monotherapy, in a Q3W regimen in combination with pembrolizumab 200 mg Q3W, or with cetuximab 400/250 mg/m² QW is available as of 18 June 2021. HAMMER Safety Review Committee have cleared SAR444245 24 µg/kg Q3W pembrolizumab combination dose level based on this data cut-off.

The dose levels tested to date for SAR444245 monotherapy administered using a Q3W schedule are 8 µg/kg (n=4), 16 µg/kg (n=6), 24 µg/kg (n=11), 32 µg/kg (n=6) and 40 µg/kg (n=2).

In combination with pembrolizumab, SAR444245 has been administered Q3W at the doses of 8 µg/kg (n=4), 16 µg/kg (n=9), 24 µg/kg (n=6), 32 µg/kg (n=1). In combination with cetuximab, SAR444245 has been administered Q3W at 16 µg/kg (n=5) or 24 µg/kg (n=5).

For monotherapy cohort, the only DLT observed to date is a Grade 3 infusion reaction (occurred on C2D1 which resolved on the same day with supportive care) reported in a patient on 32 µg/kg Q3W monotherapy.

For SAR444245 in combination with pembrolizumab 200 mg Q3W, 1 DLT (Grade 3 liver enzyme elevation with Grade 2 bilirubin elevation meeting drug-induced liver injury [DILI] criteria occurred on C1D1 which resolved after 7 days with steroids) was observed in a participant with SAR444245 24 µg/kg Q3W with pembrolizumab.

No DLTs were reported by SAR444245 cetuximab combination cohort (SAR444245 24 µg/kg Q3W).

Grade 3/4 TEAEs commonly reported by participants who received SAR444245 24 µg/kg monotherapy (n=11) include in particular Grade 4 lymphocyte count decreased/lymphopenia (7 participants, 63.6%) and Grade 3 anemia (3 participants, 27.3%) and Grade 3 dyspnea (2 participants, 18.2%). Of note, transient lymphocyte count decrease in the peripheral blood is an expected effect, consequence of T cell activation and temporary compartmental redistribution after IL-2 treatment. Nevertheless, this phenomenon is reported as an adverse event (AE) in HAMMER study.

Grade 3/4 TEAEs reported by participants who received SAR444245 24 µg/kg in combination with pembrolizumab (n=6) include Grade 4 lymphocyte count decreased (3 participants, 50.0%), Grade 3 aspartate aminotransferase (AST), alanine aminotransferase (ALT) & gamma-glutamyl transferase (GGT) increased (2 participants each for AST & ALT increased, 33.3%; 1 participant for GGT increased, 16.7%), Grade 3 blood phosphorus decreased & hypophosphatemia (1 participant each, 16.7%) and Grade 3 dyspnea (1 participant, 16.7%).

Grade 3/4 TEAEs reported by participants who received SAR444245 24 µg/kg in combination with cetuximab (n=5) include Grade 3 chills (1 participant, 20.0%) and Grade 3 abdominal pain and vomiting (1 participant for each, 20.0%).

Only 1 high grade CRS with Grade 3 hypertension, Grade 2 fever, and Grade 2/3 neurological symptoms (with 24 µg/kg Q3W, 2.6%) is reported among participants who received SAR444245

monotherapy (n=38). From participants who received SAR444245 pembrolizumab combination (n=20), Grade 3 CRS (with 16 µg/kg Q3W) is observed in 1 participant (5.0%) with Grade 3 hypotension and Grade 2 fever.

According to literature, prophylactic hydration on the dosing days could mitigate incidence and severity of hypotension as part of CRS. As HAMMER study was not mandating prophylactic hydration before January 2021, the participants who experienced CRS in HAMMER study did not receive peri-infusion hydration. Based on this learning, hydration and CRS management guidelines have been included in the Phase 2 study protocols.

With respect to PK, SAR444245 exposure increased in an approximately dose-proportional manner in the monotherapy cohorts, and no impact of anti-drug antibody (ADA) on SAR444245 PK could be identified. Also, in the combination cohort, there was no apparent impact of pembrolizumab on the PK of SAR444245.

Differently from native IL-2 and aldesleukin, SAR444245 does not have high potency at the IL-2R $\alpha/\beta/\gamma$ receptor subunit expressed on T regulatory (Treg) cells because the site-specific pegylation blocks IL-2R α engagement and demonstrates high potency at the IL2R β/γ receptor subunit expressed on CD8+ T and natural killer cells (NK). Due to this re-programmed receptor bias, SAR444245 induces proliferation of peripheral CD8+ T and NK cells and less impact on immunosuppressive Treg cells. Therefore, we closely monitored the PD change of CD8+ T, NK and Treg cells in HAMMER study as supportive information for R2PD selection.

In the SAR444245 monotherapy dose levels (8 µg/kg, 16 µg/kg, 24 µg/kg, and 32 µg/kg Q3W), the PD data suggest that a trend for dose-dependent expansion of CD8+ T cells and NK cells has been achieved. In the 8 µg/kg dose levels, the average increase in peripheral blood CD8+ T cells over baseline at 72 hours post-dose was 1.75-fold. For dose levels 16 µg/kg and 24 µg/kg, the peripheral blood CD8+ T cell expansion was 2.47 and 4.47-fold at the day 8 post-dose peak of expansion. The day 8 sample timepoint was added after the first 3 participants in the 8 µg/kg cohort were dosed.

In addition, the average increase in peripheral blood NK cells was 4.22-fold at 72 hours for 8 µg/kg. The 16 µg/kg and 24 µg/kg dose levels resulted in 5.9 and 7.67-fold NK expansion, compared to baseline at the day 8 peak expansion. Among the dose levels tested to date for SAR444245 in combination with pembrolizumab administered using Q3W schedule, we have collected available PD data for the 8 µg/kg (n=4) and 16 µg/kg cohort (n=6), in which the average increase in CD8+ T cells, compared to baseline, is 2.06-fold and 3.71-fold, respectively; and the average increase in NK cells, compared to baseline, is 6.73-fold and 13.43-fold, respectively at the peak expansion day 8. In addition, the comparison of T and NK cell expansion between █ µg/kg and █ µg/kg cohorts indicated that the anticipated maximum CD8+ T and NK cells expansion PD effect may have been achieved at █ µg/kg cohort. Based on these data, additional quantitative systems pharmacology (QSP) and popPK/PD models were developed and indicated that the increase of CD8+ T and NK cells was less than proportional with increasing dose, suggesting a flattening of the dose-response curve.

In addition, preclinical studies using human whole blood to assess the induction of cytokines showed no change in cytokine profiles when administering SAR444245 with and without

pembrolizumab. This study used SAR444245 concentration ranges that went significantly higher than current clinical dosages (0.2-4.5 µg/mL) and showed that SAR444245-induced cytokine release in human whole blood was not affected in the presence of pembrolizumab at Q3W schedule.

Considering below, Sponsor proposes to evaluate the clinical benefit of SAR444245 24 µg/kg in this Phase 2 study.

1. SAR444245 monotherapy up to 32 µg/kg Q3W, pembrolizumab combination up to 24 µg/kg Q3W and cetuximab combination 16 µg/kg Q3W are all cleared in HAMMER study.
2. Sustained relevant PD effect in blood, higher at higher dose, was documented in participants; and
3. Overlapping toxicities not expected for SAR444245 in combination with pembrolizumab or cetuximab, as suggested by safety data observed.

4.4 END OF STUDY DEFINITION

The end of the study is defined as the date of the last visit of the last participant in the study or last scheduled procedure shown in the Schedule of Activities in individual substudies for the last participant in the trial globally.

5 STUDY POPULATION

Prospective approval of protocol deviations to recruitment and enrollment criteria, also known as protocol waivers or exemptions, is not permitted.

5.1 INCLUSION CRITERIA

The inclusion criteria listed in the master protocol are only those applicable to all the participants common to all substudies. For additional substudy specific criteria, refer to the particular substudy.

Participants are eligible to be included in the study only if all of the following criteria apply for a given cohort:

Age

I 01. Participant must be ≥ 12 years of age, at the time of signing the informed consent.

See requirement specific to France in Appendix 7 ([Section 10.7](#)).

Type of participant and disease characteristics

I 02. Provision of tumor tissue:

- Disease location amenable to mandatory tumor biopsy (optional for participants ≥ 12 and <18 years of age) at baseline unless clinically unfeasible (minimum 10 slides with 4-5 micron thickness for the participants who have signed ICF [excluding screen failure participants]) and possibly at Cycle 2 Day 1. Fine needle aspirates are not acceptable. Availability of a tissue specimen from core needle or excisional biopsies, or resected tissue are required. Provision of archival tumor tissue sample obtained within 6 months (there should be no systemic anti-cancer therapy between collection of biopsy and enrollment) is allowed to replace mandatory baseline biopsy.

Note: Clinically unfeasible biopsy should be documented by a written communication from the Investigator to the Sponsor that performing a biopsy will put the wellbeing of the subject at an excessive risk.

- The Sponsor may approve the written request to enroll, on a case-by-case basis, participants with:
 - Location of the tumor not amenable to biopsy due to significant risk, OR
 - Less than required number of slides or archival tumor tissue sample collected more than 6 months prior to screening.

I 03. Measurable disease:

The participant must have relapsed or refractory disease. Measurable disease defined as at least one measurable node that must have an LDi (longest diameter) >1.5 cm and/or measurable extranodal lesion that must have a LDi >1 cm according to Lugano response criteria 2014. Tumor sites that are considered measurable must not have received prior radiotherapy, unless among them at least one is FDG-avid.

Weight (not applicable)**Sex, contraceptive/barrier method and pregnancy testing requirements**

I 04. All (male and female)

Contraceptive use by men and women should be consistent with local regulations regarding the methods of contraception for those participating in clinical studies.

a) Male participants

Male participants are eligible to participate if they agree to the following during the intervention period and for at least 3 days [corresponding to time needed to eliminate SAR444245] after the last dose of SAR444245:

- Refrain from donating or cryopreserving sperm.

PLUS either:

- Be abstinent from heterosexual intercourse as their preferred and usual lifestyle (abstinent on a long term and persistent basis) and agree to remain abstinent.

OR

- Must agree to use contraception/barrier as detailed below
- A male condom when having sexual intercourse with a woman of childbearing potential (WOCBP) who is not currently pregnant, or during homosexual intercourse. The participant should also be advised of the benefit for a female partner to use a highly effective method of contraception (as described in Appendix 4 Contraceptive and barrier requirements [[Section 10.4](#)]) as a condom may break or leak when having sexual intercourse with a woman of childbearing potential (WOCBP) who is not currently pregnant.

b) Female participants

A female participant is eligible to participate if she is not pregnant or breastfeeding, and at least one of the following conditions applies:

- Is not a woman of childbearing potential (WOCBP).

OR

- Is a WOCBP and agrees to use a contraceptive method that is highly effective (with a failure rate of $<1\%$ per year), with low user dependency, as described in Appendix 4 ([Section 10.4](#)) during the intervention period (to be effective before starting the

intervention) and for at least 120 days (or refer to the individual substudy protocol [corresponding to the time needed to eliminate any study intervention(s)] after the last dose of study intervention and agrees not to donate or cryopreserve eggs (ova, oocytes) for the purpose of reproduction during this period.

- A WOCBP must have a negative highly sensitive pregnancy test (as required by local regulations) within 72 hours before the first dose of study intervention.
- Additional requirements for pregnancy testing during and after study intervention are located in Appendix 4 ([Section 10.4](#)).
- The Investigator is responsible for review of medical history, menstrual history, and recent sexual activity to decrease the risk for inclusion of a woman with an early undetected pregnancy.

Informed Consent

I 05. Capable of giving signed informed consent as described in Appendix 1 which includes compliance with the requirements and restrictions listed in the informed consent form (ICF) and in this protocol. For participant below legal age to provide ICF, a specific ICF must be signed by the participant's legally authorized representative.

5.2 EXCLUSION CRITERIA

Participants are excluded from the study if any of the following criteria apply. For additional individual substudy specific criteria, refer to the particular substudy.

Medical conditions

- E 01. Eastern Cooperative Oncology Group (ECOG) performance status of ≥ 2 (≥ 16 years old). Lansky Scale (< 16 years old) $\leq 60\%$.
- E 02. Lymphomatous involvement of the central nervous system.
- E 03. Predicted life expectancy ≤ 3 months.
- E 04. History of solid organ transplant.
- E 05. Treatment-related immune-mediated (or immune-related) AEs from immune-modulatory agents (including but not limited to anti-PD-1/PD-L1 agents and anti-cytotoxic T lymphocyte associated protein 4 monoclonal antibodies) that caused permanent discontinuation of the agent, or that were Grade 4 in severity.
- E 06. Prior IV or subcutaneous anticancer therapy, investigational agent, major surgery within 21 days prior to initiation of IMP; oral anticancer therapy within 5 half-lives or completed palliative radiotherapy within 21 days prior to initiation of IMP.

- E 07. Uncontrolled pleural/peritoneal effusion, pericardial effusion or ascites requiring recurrent drainage procedures (once monthly or more frequently).
- E 08. Comorbidity requiring corticosteroid therapy (>10 mg prednisone/day or equivalent) within 14 days of IMP initiation. Inhaled or topical steroids are permitted, provided that they are not for treatment of an autoimmune disorder. Participants who require a brief course of steroids (eg, as prophylaxis for imaging studies due to hypersensitivity to contrast agents or as premedication for erythrocyte or platelet transfusions) are not excluded.
- E 09. Antibiotic use (excluding topical antibiotics) \leq 14 days prior to the first dose of IMP, or any serious systemic fungal, bacterial, viral (excluding viral infection settings as described in E 16), or other infection that is not controlled. Participants who require prophylactic antibiotics because of chronic immunodeficiency will be allowed.
- E 10. Severe or unstable cardiac condition within 6 months prior to starting study treatment, such as congestive heart failure (New York Heart Association Class III or IV), cardiac bypass surgery or coronary artery stent placement, angioplasty, left ventricular ejection fraction (LVEF) below 50%, unstable angina, medically uncontrolled hypertension (eg, \geq 160 mmHg systolic or \geq 100 mmHg diastolic), uncontrolled cardiac arrhythmia requiring medication (\geq Grade 2, according to NCI-CTCAE v5.0), or myocardial infarction.
- E 11. Ongoing AEs caused by any prior anticancer therapy \geq Grade 2 (NCI-CTCAE Version 5.0). Participants with Grade 2 peripheral neuropathy, or Grade 2 alopecia are permitted. Participants with endocrine-related AEs Grade \leq 2 requiring treatment or hormone replacement may be eligible.

Note: If the participant had major surgery, the participant must have recovered adequately from the procedure and/or any complications from the surgery prior to starting study intervention.

Note: please refer to the individual substudy protocol for cohort specific requirement.

- E 12. Active, known, or suspected autoimmune disease that has required systemic treatment in the past 2 years (ie, with use of disease modifying agents, corticosteroids or immunosuppressive drugs), except controlled by replacement therapy (eg, thyroxine, insulin, or physiologic corticosteroid replacement therapy for adrenal or pituitary insufficiency, etc). The following are not exclusionary: vitiligo, childhood asthma that has resolved, psoriasis that does not require systemic treatment.
- E 13. History of (non-infectious) pneumonitis / interstitial lung disease that required steroids or has current pneumonitis / interstitial lung disease.
- E 14. History of thoracic radiation therapy of >30 Gy within 6 months of the first dose of trial treatment.

E 15. Receipt of a live or live attenuated virus vaccine within 28 days of planned treatment start. Seasonal flu vaccines or SARS-CoV-2 vaccines that do not contain live virus are permitted.

E 16. Human immunodeficiency virus (HIV)-infected participants with a history of Kaposi sarcoma and/or Multicentric Castleman Disease or known uncontrolled infection with HIV. HIV-infected participants must be on anti-retroviral therapy (ART) and have a well-controlled HIV infection/disease defined as:

- Participants on ART must have a CD4+ T-cell count >350 cells/mm³ at time of screening.
- Participants on ART must have achieved and maintained virologic suppression defined as confirmed HIV RNA level below 50 copies/mL or the lower limit of qualification (below the limit of detection) using the locally available assay at the time of screening and for at least 12 weeks prior to screening.
- Participants on ART must have been on a stable regimen, without changes in drugs or dose modification, for at least 4 weeks prior to study entry (Day 1).
- Combination ART regimen must not contain any antiretroviral medications other than: abacavir, dolutegravir, emtricitabine, lamivudine, raltegravir, rilpivirine, or tenofovir. HIV serology will be tested at screening for participants in France (see details and specific instructions in [Section 10.2](#) and [Section 10.7](#)).

E 17. Known uncontrolled hepatitis B infection, known untreated current hepatitis C infection, active tuberculosis, SARS-CoV-2 infection, or severe infection requiring parenteral antibiotic treatment.

- To control HBV infection, participants with positive HBsAg should have started anti-HBV therapy before initiation of IMP. Antiviral therapy for HBV must be given for at least 4 weeks and HBV viral load must be less than 100 IU/mL prior to first dose of study drug. Participants on active HBV therapy with viral loads under 100 IU/mL should stay on the same therapy throughout study treatment.
- Participants who are positive for anti-hepatitis B core antibody HBC, negative for hepatitis B surface antigen (HBsAg), and negative or positive for anti-hepatitis B surface antibody (HBs), and who have an HBV viral load under 100 IU/mL, do not require HBV anti-viral prophylaxis.
- Participants with past or ongoing hepatitis C virus (HCV) infection will be eligible for the study. The treated participants must have completed their treatment at least 1 month prior to starting study intervention. Participants with positive HCV antibody and undetectable HCV RNA without anti-HCV therapy are eligible.
- Participants with a history of SARS-CoV-2 infection must have completed clinical recovery at least 1 month prior to enrollment and no longer have a positive PCR test for SARS-CoV-2 at the time of enrollment.

E 18. Known second malignancy either progressing or requiring active treatment within the last 3 years. Participants with basal cell carcinoma of the skin, squamous cell carcinoma of the

skin, or carcinoma in situ (eg, breast carcinoma, cervical cancer in situ) that have undergone potentially curative therapy are not excluded.

- E 19. Known severe hypersensitivity (\geq Grade 3) to or contraindication for the use of any study intervention or components thereof, including premedication to be administered in this study, as well as PEG or any pegylated drug and *E. coli*-derived protein.
- E 20. Participants with baseline oxygen saturation (SpO_2) \leq 92% (without oxygen therapy).

Prior/concomitant therapy

- E 21. Has received prior IL2-based anticancer treatment.
- E 22. Is unable or unwilling to take premedication.
- E 23. Deleted by protocol amendment 01.
- E 24. Deleted by protocol amendment 01.

Prior/concurrent clinical study experience

- E 25. Current enrollment or past participation in a study of an investigational treatment or has used an investigational device within 28 days prior to the first dose of study treatment.

Note: Participants who have entered the follow-up phase of an investigational study may participate as long as it has been 28 days after the last dose of the previous investigational treatment.

Organ and bone marrow function

- E 26. Absolute neutrophil count $<1000/\mu\text{L}$ ($1 \times 10^9/\text{L}$) (after at least one week off G-CSF).
- E 27. Platelets $<50 \times 10^3/\mu\text{L}$ (after at least 3 days without platelet transfusion).
- E 28. Hemoglobin $<9 \text{ g/dL}$ or $<5.6 \text{ mmol/L}$ (after at least 1 week without packed red blood cell [pRBC] transfusion. Participants can be on stable dose of erythropoietin (\geq approximately 3 months)).
- E 29. Total bilirubin $>1.5 \times$ upper limit of normal (ULN) unless direct bilirubin \leq ULN (participants with known Gilbert disease who have serum bilirubin level $\leq 3 \times$ ULN may be enrolled).
- E 30. Aspartate aminotransferase (AST) and/or alanine aminotransferase (ALT) $>2.5 \times$ ULN (or $>5 \times$ ULN for participants with lymphoma involving the liver).
- E 31. Estimated glomerular filtration rate (eGFR) $<50 \text{ mL/min}/1.73 \text{ m}^2$ (Modification of Diet in Renal Disease [MDRD] Formula, see [Section 10.2 Appendix 2](#)).

E 32. International Normalized Ratio (INR) or Prothrombin Time (PT) (or Activated Partial Thromboplastin Time [aPTT]) $>1.5 \times \text{ULN}$ unless the participant is receiving anticoagulant therapy as long as PT or aPTT is within therapeutic range of intended use of anticoagulants.

Other exclusions

E 33. Individuals accommodated in an institution because of regulatory or legal order; prisoners or participants who are legally institutionalized.

E 34. Any country-related specific regulation that would prevent the participant from entering the study - see [Section 10.7 Appendix 7](#) (country-specific requirements).

E 35. Participant not suitable for participation, whatever the reason, as judged by the Investigator, including medical or clinical conditions, or participants potentially at risk of noncompliance to study procedures.

E 36. Participants are employees of the clinical study site or other individuals directly involved in the conduct of the study, or immediate family members of such individuals (in conjunction with section 1.61 of the ICH-GCP Ordinance E6).

E 37. Any specific situation during study implementation/course that may raise ethics considerations.

E 38. History or current evidence of any condition, therapy, or laboratory abnormality that might confound the results of the trial, interfere with the subject's participation for the full duration of the trial, or is not in the best interest of the subject to participate, in the opinion of the treating Investigator.

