10.2 APPENDIX 2: CLINICAL LABORATORY TESTS

- The tests detailed in [Table 6](#) will be performed by the local laboratory.
- Protocol-specific requirements for inclusion or exclusion of participants are detailed in [Section 5](#).
- Additional tests may be performed at any time during the study as determined necessary by the Investigator or required by local regulations.

Table 6 - Protocol-required laboratory assessments

Laboratory tests	Parameters
Hematology ^a	Platelet count Hemoglobin Hematocrit White blood cell (WBC) count with differential: Neutrophils Lymphocytes Monocytes Eosinophils Basophils
Clinical chemistry ^a	Urea or blood urea nitrogen (BUN) Creatinine and eGFR (MDRD formula ^b) Glucose Potassium Sodium Corrected Calcium Phosphate Chloride Magnesium Bicarbonate ^c Aspartate aminotransferase (AST)/ Serum glutamic-oxaloacetic transaminase (SGOT) Alanine aminotransferase (ALT)/ Serum glutamic-pyruvic transaminase (SGPT) Alkaline phosphatase Total and direct bilirubin Total protein Lactate dehydrogenase (LDH) Albumin Amylase Lipase
Endocrine function tests ^d	Thyroid-stimulating hormone (TSH) Tri-iodothyronine (T3) Free thyroxine (FT4) Cortisol (preferably in the morning)
Coagulation	International normalized ratio (INR) or Prothrombin Time (PT) (or Activated Partial Thromboplastin Time [aPTT])
Routine urinalysis	
 Specific gravity, pH, glucose, protein, blood, ketones, and leukocytes by dipstick Microscopic examination (if blood or protein is abnormal)
Other screening tests	
 Follicle-stimulating hormone and estradiol may be used to confirm a postmenopausal state in women not using hormonal contraception or hormonal replacement therapy (HRT) Highly sensitive serum or urine human chorionic gonadotropin (hCG) pregnancy test (as needed for women of childbearing potential) ^e Serology (hepatitis B surface antigen [HBsAg], hepatitis C virus antibody), Hepatitis

B viral load, HCV RNA level, CD4 counts & HIV viral Load^f

- Troponin
- The results of each test must be entered into the e-CRF

NOTES:

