- f Participants with known HIV infection under antiretroviral treatment should have HIV viral load & CD4+ count done at screening to confirm controlled infection. Participants with known HBV hepatitis under treatment must have viral load determined at baseline to document controlled infection. Participants with positive serology against HCV must have determination of HCV RNA levels. The need for additional testing due to positive test results will be at the discretion of the Investigator. HIV serology at screening will be tested in any countries where mandatory as per local requirements (see [Section 10.7](#)).

Investigators must document their review of each laboratory safety report.

10.3 APPENDIX 3: AES AND SAES: DEFINITIONS AND PROCEDURES FOR RECORDING, EVALUATING, FOLLOW-UP, AND REPORTING

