- m For participants with known HIV, hepatitis B and hepatitis C infection under antiviral treatment to confirm controlled infection, and for all participants in France (see details and specific instructions in Section 10.2 and Section 10.7 in the master protocol, and [Section 10.7](#) in this substudy 01).
- n Prior medications that are received within 30 days before the first dose of IMP.
- o Hospitalization for 48 h for safety run-in participants or for participants with a high tumor burden or at investigator's discretion.
- p AE/SAE assessment: Severity will be graded according to NCI-CTCAE v 5. ICANS and CRS will be graded using ASTCT criteria integrated with central laboratory cytokine results ([2](#)).
- q The initial tumor imaging FDG-PET CT and/or MRI will be performed within 28 days prior to C1D1. Scans performed as part of routine clinical management are acceptable for use as the screening scan if they are of diagnostic quality and performed within 28 days prior to the date of enrollment. On study imaging will be performed every 9 weeks (63 \pm 7 days) after the date of first IMP and if clinically indicated. FDG-PET must be performed for the 9-week and 18-week on-treatment assessments. Imaging studies should follow calendar days and should not be adjusted for delays in cycle starts or extension. The same imaging technique should be used in a participant throughout the trial. After Week 45 tumor imaging should be performed every 12 weeks (84 \pm 7 days). CT scan of the chest, abdomen, pelvis and any other locations with suspicion or evidence of disease involvement is required for the baseline and follow-up assessments.
- r If a tumor biopsy was obtained from a target lesion during eligibility assessment, it is preferred to obtain a new baseline scan. Tumor biopsy should be considered for new lesions if their pathologic etiology is ambiguous.
- s Brain CT/MRI: To be performed if clinically indicated.

Amended Clinical Trial Protocol 01 (Substudy 01)
SAR444245-ACT16941

[figure not shown]
28-Apr-2022
Version number: 1

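### Criterion E 17 both excludes and admits known untreated ongoing hepatitis C, and SoA footnote m does not schedule the hepatitis tests that E 17 and Table 6 rely on

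*Protocol*

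**What the plan says.** **Eligibility (master protocol, Section 5.2).** The section works on an any-one-applies basis: "Participants are excluded from the study if any of the following criteria apply". The opening sentence of E 17 lists "Known uncontrolled hepatitis B infection" and "known untreated current hepatitis C infection". Its third bullet then states "Participants with past or ongoing hepatitis C virus (HCV) infection will be eligible for the study", followed by "The treated participants must have completed their treatment at least 1 month prior to starting study intervention". The bullet closes by accepting participants who are HCV antibody positive, have undetectable RNA and have had no anti-HCV therapy. The two hepatitis B bullets are keyed to HBsAg, to anti-HBc and to HBV viral load.

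**Laboratory list (master protocol, Section 10.2, Table 6).** Among the other screening tests is an entry that begins "Serology (hepatitis B surface antigen [HBsAg], hepatitis C virus antibody), Hepatitis" and continues to HBV viral load, HCV RNA, CD4 count and HIV viral load. Footnote f adds "Participants with positive serology against HCV must have determination of HCV RNA levels" and asks for a baseline viral load in known, treated HBV. Anti-HBc is not listed.

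**Schedule (Section 1.3 of Substudy 01 and of Substudy 03).** The screening cell of the row for hepatitis serology, CD4+ counts and viral load carries footnote m, which reads the same in both: "For participants with known HIV, hepatitis B and hepatitis C infection under antiviral treatment to confirm controlled infection, and for all participants in France". It refers the reader to the laboratory and country-specific sections. After screening, the row is marked as clinically indicated.

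**The concern.** Two things do not fit together.

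First, within E 17, one participant gets opposite answers depending on which sentence the site reads. Section 5 of the master protocol does not allow waivers, so the site cannot settle the matter case by case.

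Second, several E 17 bullets decide status from test results, but the schedule does not order those tests for the people to whom the bullets apply. Section 8.2.4 sends sites to Appendix 2 for the list of tests and to the SoA for their timing, and requires tests to follow the SoA. A site that obeys the SoA and a site that works from Table 6 and footnote f would screen differently.

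At stake is whether sites enrol by the same rule, and whether the baseline hepatitis status that E 17 presupposes is on file.

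**Working it through.** No figure in the plan depends on this point, so the check is textual. Each hepatitis status is run through E 17, through Table 6 with footnote f, and through footnote m as it reads for a participant outside France.

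| Status | E 17 | Table 6 and footnote f | SoA footnote m |
|---|---|---|---|
| 1. Known HCV, untreated, RNA positive | Opening sentence excludes; third bullet admits | RNA after positive serology | Not scheduled |
| 2. HCV, on treatment now | Bullet's first sentence admits; its second bars until 1 month after completion | RNA after positive serology | Scheduled |
| 3. HCV, treatment completed at least 1 month ago | Eligible | RNA after positive serology | Not scheduled |
| 4. HCV antibody positive, RNA undetectable, never treated | Eligible | RNA after positive serology | Not scheduled |
| 5. Known HBV, on treatment | At least 4 weeks of therapy and viral load below 100 IU/mL | Baseline viral load | Scheduled |
| 6. Anti-HBc positive, HBsAg negative, untreated | Bullet needs a viral load under 100 IU/mL | Anti-HBc not listed; footnote f asks for a load only in known, treated HBV | Not scheduled |
| 7. HBV or HCV not known | Not reached by the opening sentence, which says known | HBsAg and HCV antibody listed | Not scheduled |

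Reading across:

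- **Row 1** is a direct contradiction inside one criterion.
- **Rows 2 to 4** show the mismatch for hepatitis C. The only HCV group that footnote m schedules is the one still on treatment, which E 17 does not yet admit. The two groups that E 17 clearly admits (rows 3 and 4) have no scheduled antibody or RNA test.
- **Row 5** is consistent in all three places.
- **Row 6** shows that the bullet on anti-HBc depends on a test listed in neither place.
- **Row 7** is a difference between Table 6 and footnote m. It does not conflict with the opening sentence of E 17, which concerns known infection only.

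**France.** Read literally, footnote m extends the whole row to every participant in France. The country-specific sections it relies on (Section 10.7 of the master protocol and of each substudy) require HIV serology there and do not mention hepatitis. The documents therefore leave it open whether the clause covers hepatitis.

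**The case against.** **The opening sentence could simply govern.** Any criterion that applies excludes, so a site might treat row 1 as excluded. That is a workable default. But the bullet is an explicit statement of eligibility inside the same criterion, and a site can as easily read it as the exception. A narrower sense of ongoing, meaning treated but not yet cleared, would remove the conflict, but it is not written.

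**The exclusions turn on known infection.** This stands. Both hepatitis exclusions in the opening sentence can be applied from history, and a schedule limited to known infection is not in itself at odds with them. A reader might infer that the hepatitis rules as a whole cannot be applied; row 5 and the word known show that this goes too far.

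**Listing in Table 6 does not make a test universal.** This also stands in part. The same block of Table 6 holds conditional items, such as hormone tests that may be used and a pregnancy test as needed. A reader might infer that serology is meant for everyone, but the documents do not say so outright. They do say that RNA follows a positive HCV serology, and footnote m schedules no such serology for rows 3 and 4.

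**Untested does not mean untestable.** Appendix 2 allows additional tests at any time, the SoA row continues as clinically indicated, E 30 screens ALT and AST, and E 35 and E 38 leave room for investigator judgement. These soften the practical effect but do not say which text governs.

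**Conclusion.** The point holds as an internal inconsistency. One class of participant (known, untreated, RNA-positive HCV) has two stated statuses. Footnote m in both substudies is out of step with E 17, Table 6 and footnote f, most clearly for hepatitis C, where it schedules only a group that is not yet admissible. This rests on the plain wording of the sections. It assumes no infection rate, and it leaves sample size, confidence intervals and every stated statistic unchanged.

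Three stronger conclusions might be inferred and are not supported:

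- **A distorted dose decision.** In the master protocol's Table 2, at 6 evaluable participants, 2 DLTs means stay and 3 means de-escalate, so one misattributed hepatic event might seem decisive. But the hepatic DLT in Section 4.1 already requires that there be no other cause, such as viral infection, and testing at the time of the event can establish that. The Study Board may also decide otherwise.
- **A 22% to 72% chance of the problem arising.** The 22.2% and 72.3% in the sample size sections are probabilities of seeing an adverse event with 1% or 5% incidence in 25 participants. They are not hepatitis prevalences, which the documents do not give, and they do not refer to the 6 participants behind the dose decision. At the same assumed 1% to 5%, the chance of at least one infected participant among 6 would be 1 − 0.99^6 = 5.9% to 1 − 0.95^6 = 26.5%, and that is still not the chance of a misattributed event.
- **Different hepatitis screening in France.** The country-specific sections require only HIV serology, so a national difference in hepatitis testing is not established.

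**What to change.** 1. In E 17, reconcile the opening sentence with the third bullet so that known, untreated, ongoing HCV has one stated status.
2. In footnote m of both SoAs, reconcile the condition on antiviral treatment with E 17 (including its completed-treatment sentence for HCV), with Table 6 and with footnote f. The tests that the E 17 bullets depend on, including anti-HBc, should then be listed and scheduled the same way in all places.
3. State whether the France clause in footnote m covers hepatitis or only HIV serology. When editing the Substudy 03 footnote, also check its pointer to that substudy's Section 10.6, since country requirements stand in 10.7.

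Which eligibility rule and which testing rule apply is for the sponsor to settle; the request is only that the passages agree. The cost is wording in one criterion and one footnote in two schedules, with a matching line in Table 6 if anti-HBc is kept. HBsAg and HCV antibody are already in Table 6. Depending on the rule chosen, there may be a few more screening results and an occasional screen failure. No analysis needs to change.
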